7.1.2 Labeling and Packaging of IMP

IMP will be labelled according to the legal requirements and packaged into individual subject kits, each containing 2 bottles of NOV03 or saline solution. See [Section 7.1.4](#) for details regarding dispensation to subjects.

In compliance with the Code of Federal Regulations 21 part 312, section 312.6, the labels for the IMP shall be comprised of:

- Protocol number
- Kit Number
- Investigational new drug statement
- Storage conditions
- Name and address of the sponsor

7.1.3 IMP Storage

The IMPs must be stored in a secure area accessible only to the investigator or pharmacist and his/her designees. IMPs must be stored **at room temperature** under temperature-monitored conditions and must not be refrigerated. Subjects should be instructed to store IMP at room temperature and out of children's reach at home. Subjects should not use a dispensed bottle that has been opened for more than 30 days.

7.1.4 IMP Dispensation

- The dedicated dosing coordinator is responsible for dispensing the IMP and supervision of first dose administration at Visit 1.
- The IMPs must only be distributed to subjects properly qualified under this protocol to receive IMP.
- IMP will be provided to the clinical sites as subject kits containing 2 bottles of NOV03 or saline solution.
- At the end of Visit 1, qualified subjects will be randomized and a kit of IMP containing 2 bottles for each subject will be assigned using IRS. The first dose of IMP will be administered at the clinical site.
- At Visits 1 and 2 the subject will receive **one** subject kit.
- At Visit 3 the subject will receive **two** subject kits.
- At Visits 2, 3 and 4 used/unused IMP will be collected from subjects for drug accountability by the dedicated dosing coordinator.

Subjects will be instructed to immediately contact the site if there is any problem with the IMP, e.g. kit/bottle(s) was damaged or lost or if the open bottle was dropped. In case the subject needs a replacement bottle of IMP, the next bottle from the kit can be used by the subject. If no bottle remains in the kit, a new kit will be assigned to the subject using IRS.

7.1.5 Instructions for Use and Administration

At Visit 1 subjects will be instructed by the dedicated dosing coordinator on appropriate hygiene and eye drop dosing technique. Subjects will self-administer NOV03 or saline eye

drops in each lower cul-de-sac of each eye as shown in Appendix 2 under the supervision of the dedicated dosing coordinator on Day 1 (Visit 1).

Subsequent eye drops on Day 1 are to be instilled by the subjects according to detailed written instructions. Subjects will be instructed to instill their drops into both eyes QID for the duration of the trial. Clinic staff will coach the subjects to dose themselves at approximately the same time every day e.g., morning, lunch time/mid-day, afternoon/early evening, and at bedtime. If a dose is missed, then the next dose should be administered on time.

The dedicated dosing coordinator will inform subjects on how to store IMP (see [Section 7.1.3](#)) and dose IMP and how to complete their dosing diary.

Dosing should be continued until the day of the next Visit (should be at least 2 hours before first ophthalmic examination).

The bottles are designed for multiple use. Subjects will be instructed to only open one bottle at a time. They should be instructed not to discard the empty bottles but keep them in the kit box and return them at their next visit in the kit box. Subjects will record dosing in their dosing diary. Subjects will be instructed not to show the assigned IMP to the Investigator or site staff other than the dedicated dosing coordinator, unless instructed to do so.

7.2 IMP Accountability

The dedicated dosing coordinator at each site must keep an accurate accounting of IMPs received from the supplier by maintaining a detailed inventory. IMP shipment records will be verified and accountability performed by comparing the IMP shipment inventory sheet to the actual quantity of used/unused IMP bottles received at the site.

Accurate records of receipt and disposition of the IMP (e.g. dates, quantity, subject number, kits used, kits unused, etc.) must be maintained by the dedicated dosing coordinator at each site. This includes the amount dispensed to subjects, amount returned to the site by the subjects, and the amount returned to the sponsor or designee upon completion of the trial.

Investigational trial medication orders, records of receipts, dispensing records, and inventory forms will be examined and reconciled by the dedicated dosing coordinator. At each visit, subjects will return all bottles to clinic staff for accountability purposes. Accountability will be ascertained by performing reconciliation between the amount of IMP cartons (kits and their components) sent to the site, the amount used and unused at the time of reconciliation. All investigational trial medication that is dispensed during the course of the trial must be accounted for on an IMP accountability form. No IMP kits or bottles will be returned to the sponsor prior to full accountability by sponsor's monitor.

7.3 IMP Handling and Return

Unless otherwise directed, at the end of the trial all returned (used and unused) IMP must be directly shipped from the clinical site to the sponsor for destruction of the medications. **Note: The medications should not be disposed or returned prior to full accountability by the sponsor's monitor.** The clinical site will include a copy of all completed drug disposition forms with the IMP to the sponsor after full accountability is completed.

7.4 IMP Masking

Investigational drug and control will be provided in identical bottles and labels to ensure the double-masked character of the trial. The Investigator/site staff and Bausch & Lomb, Incorporated. personnel or designee(s) involved in the conduct of the trial will be masked to the IMP. Clinical Trial Material Supply Chain are unmasked designee.

Due to physicochemical differences between NOV03 and saline, there will be a dedicated dosing coordinator who will be responsible for the handling of IMP and activities (such as dispensation, collection, accountability) surrounding the use of IMP.

Each site must have a dedicated dosing coordinator that will be responsible for:

- all IMP dispensation and accountability,
- daily diary dosing education/review,
- all discussions with study subjects related to IMP,
- the administration of the Eyedrop Acceptability and Instillation Comfort Questionnaires.

This designee shall not participate in any other trial procedures and not report this information to other staff. Subjects will be instructed to administer the IMP out of the sight of the Investigator or site staff other than the dedicated dosing coordinator. Subjects are not to show or discuss the properties of the assigned IMP to the Investigator or site staff other than the dedicated dosing coordinator, unless instructed to do so.

7.5 Other Trial Supplies

Diaries, Questionnaires, Urine Pregnancy Tests, Meibomian Gland Evaluator stick, Schirmer's test strips, sodium fluorescein, will be provided to sites. Respective instructions are available in Appendix 3 and manual of operations.

8 TRIAL METHODS AND PROCEDURES

8.1 Concurrent Medications and Therapies

The use of any concurrent medication, prescription or over-the-counter, is to be recorded on the subject's source document and corresponding eCRF along with the reason the medication was taken. Concurrent or previous medications are to be recorded for 60 days prior to Visit 0. Any physical therapies, or surgeries are to be documented for 6 months prior to Visit 0.

Therapy considered necessary for the subject's welfare that will not interfere with the evaluation of the study medication may be given at the discretion of the Investigator and in consultation with the medical monitor. If there is any question as to whether the medication may interfere, the investigator should contact the medical monitor or sponsor. Whenever possible, medications should be administered in dosages that remain constant throughout the study duration.

Physical therapies such as lid scrubs, lid wipes, warm compresses, systemic antibiotics (such as tetracyclines) and oral supplements for treatment of ocular conditions must be stable within the last 30 days prior to Visit 1 and should be maintained stable throughout the trial. Changes in those therapies or initiation of such therapies should be recorded on the subject's source document and corresponding eCRF.

8.4 Examination Procedures

8.4.1 Procedures to be performed at each trial visit with regard to trial objective(s)

See Appendix 1 for a schedule of visits and measurements in recommended order. Appendix 3 describes the eye examinations. These should not be done earlier than 2 hours after IMP instillation. If possible the same investigator/coordinator should perform the assessments for an individual subject. Primary endpoint assessments at Baseline Visit 1 (Day 1) and Visit 4 (Day 57) should be done preferably on the same time of the day.

The dedicated dosing coordinator will perform tasks as described in [Section 7.4](#).

Visit 0 (Up to 14 days before Visit 1): Screening

- Informed consent / HIPAA;
- Demographic data and medical / medication history;
- Review of inclusion / exclusion criteria;
- Urine pregnancy test;
- Ocular Surface Disease Index (OSDI[©]) questionnaire;
- Visual acuity (ETDRS);
- Slit-Lamp biomicroscopy;
- Tear Film Break-up Time (TFBUT);
- Fluorescein staining (NEI scale);
- Meibomian gland assessment (MGD score) (wait 5 min prior start of Schirmer's test);
- Schirmer's test I (without anesthesia);
- Intraocular pressure;
- Dilated fundoscopy;
- Non-leading AE questioning (Adverse event query);
- Qualified subjects will be scheduled for Visit 1.

Visit 1 (Day 1): Baseline/Randomization

- Previous/Concomitant Medication;
- Review of inclusion / exclusion criteria;
- Urine pregnancy test;
- Dryness Score (VAS Severity of Dryness);
- VAS for burning/stinging, sticky feeling, foreign body sensation, itching, blurred vision, sensitivity to light, pain, frequency of dryness, and awareness of dry eye symptoms;
- Ocular Surface Disease Index (OSDI[©]) questionnaire;
- Visual acuity (ETDRS);
- Slit-Lamp biomicroscopy;
- Tear Film Break-up Time (TFBUT);
- Fluorescein staining (NEI scale);
- Meibomian gland assessment (MGD score) (wait 5 min before start of Schirmer's test);
- Schirmer's test I (without anesthesia);
- Randomization;
- In-office dose of IMP;
- Instillation comfort questionnaire;
- Non-leading AE questioning (Adverse event query);
- Dispensation of dosing diary;
- Drug dispensation of one kit for self-administered dosing until Visit 2;
 - Subjects will be instructed on how to administer IMP;
 - Subjects will be instructed to dose with IMP on the day of their next visit at least 2 hours before the start of their visit (Visit 2);
 - Subjects will be instructed on how to complete the dosing diary.

Visit 2 (Day 15 ± 1), Visit 3 (Day 29 ± 2):

- At the beginning of the visit the subject will be asked about the time of last dose. Assessments should be performed at least 2 hours after last dose of IMP;
- Collection and review of IMP and dosing diary;
 - Calculate subject compliance with doses in the subject diary as described in [Section 8.5](#) and re-educate subject as necessary.
- Concomitant medication update;
- Dryness Score (VAS Severity of Dryness);
- VAS for burning/stinging, sticky feeling, foreign body sensation, itching, blurred vision, sensitivity to light, pain, frequency of dryness, and awareness of dry eye symptoms;
- Ocular Surface Disease Index (OSDI[©]) questionnaire;
- Visual acuity (ETDRS);
- Slit-Lamp biomicroscopy;
- Fluorescein staining (NEI scale);
- Non-leading AE questioning (Adverse event query);
- Re-dispensation of dosing diary;

Visit 2 Drug dispensation of one kit for self-administered dosing until Visit 3;

- Subjects will be instructed on how to administer IMP;
- Subjects will be instructed to dose with IMP on the day of their next visit at least 2 hours before the start of their visit (Visit 3);
- Subjects will be instructed on how to complete the dosing diary.

Visit 3 Drug dispensation of two kits for self-administered dosing until Visit 4;

- Subjects will be instructed on how to administer IMP;
- Subjects will be instructed to dose with IMP on the day of their next visit at least 2 hours before the start of their visit (Visit 4);
- Subjects will be instructed on how to complete the dosing diary.

Visit 4 (Day 57 ± 2) or ET:

- At the beginning of the visit the subject will be asked about the time of last dose. Assessments should be performed at least 2 hours after last dose of IMP;
- Collection and review of IMP and diary;
- Concomitant medication update;
- Urine pregnancy test;
- Dryness Score (VAS Severity of Dryness);
- VAS for burning/stinging, sticky feeling, foreign body sensation, itching, blurred vision, sensitivity to light, pain, frequency of dryness, and awareness of dry eye symptoms;
- Ocular Surface Disease Index (OSDI[©]) questionnaire;
- Eyedrop acceptability questionnaire;
- Visual acuity (ETDRS);
- Slit-lamp biomicroscopy;
- Tear Film Break-up Time (TFBUT);
- Fluorescein staining (NEI scale);
- Meibomian gland assessment (MGD score) (wait 5 min before start of Schirmer's test);
- Schirmer's test I (without anesthesia);
- Intraocular pressure;
- Dilated fundoscopy;
- Non-leading AE questioning (Adverse event query);
- Trial exit.

8.4.2 Early Termination/Discontinuation

The following data from subjects discontinuing before randomization (i.e. screen failures) will be captured in the eCRF:

- Demographics
- AEs / SAEs
- Reason for discontinuation (including applicable assessment results)

If a randomized subject is discontinued from the trial prior to Visit 4 (Day 57 ± 2) and not willing to perform all subsequent visits and assessments, then all evaluations planned for

Visit 4 should be performed on the day of discontinuation (early termination) or at the discretion of the investigator.

Randomized and dosed subjects who discontinue treatment for any reason will be encouraged to undergo all subsequent trial visits and assessments.

Data from subjects discontinuing after randomization will be captured completely in the eCRF including Early Termination Visit and reason for discontinuation.

8.4.3 Unscheduled Visits

An unscheduled visit may be performed during the course of the trial in order to ensure subject safety and/or to dispense additional IMP if necessary (i.e. damaged/lost or subject ran out of IMP in between visits). All procedures performed at an unscheduled visit will be recorded in the source documents and on the unscheduled visit eCRF pages. Any unscheduled visit procedure listed in the eCRF that is not performed should be indicated as “not done.”

Evaluations that may be conducted at an unscheduled visit include:

- Slit-Lamp biomicroscopy;
- Visual acuity;
- Intraocular pressure;
- Dilated fundoscopy;
- Urine pregnancy test (for women of childbearing potential);
- Assessment of AEs;
- Assessment of concomitant medications and/or treatments; and
- Any other assessments needed in the judgment of the investigator.

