6.5.8.2 Analysis Visits

The eCRF nominal study visits will be used for analysis. For subjects who withdraw from the study, if they withdraw at a regular scheduled visit, the data collected at the time of withdrawal will be summarized under the regular visit; if they withdraw between scheduled visits, the early termination visit will be treated as an unscheduled visit. For the purposes of table summarization, the first visit for each nominal study visit will be used.

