6.5.9.4 Other Safety Measurements

Visual acuity, slit-lamp biomicroscopy, dilated fundoscopy, and intraocular pressure will be summarized by treatment group and visit using descriptive statistics in SAF. Changes from baseline will also be summarized where appropriate. For assessments performed by eye, study eye and fellow eye will be summarized separately.

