6.5.9.4.4 Intraocular Pressure

Intraocular pressure (IOP) will be measured in each eye by contact tonometry by the examiner and the results will be recorded in mmHg at screening, Visit 4 and early termination. A single measurement will be made to obtain a determination of IOP. Descriptive statistics for the IOP measurement will be presented for study eye and fellow eye by treatment and overall at baseline and all post-baseline visits in the SAF. Changes from baseline will also be summarized.

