14422 Summary of Fellow Eye Slit-lamp Biomicroscopy Results by Location and Visit – SAF Worsening Shifts in Study Eye Slit-lamp Biomicroscopy Results—SAF 14.4.3.1 Worsening Shifts in Fellow Eye Slit-lamp Biomicroscopy Results—SAF 14.4.3.2 Summary of Study Eve Dilated Fundoscopy Results by Location and Visit – 14.4.4.1 **SAF** 14442 Summary of Fellow Eye Dilated Fundoscopy Results by Location and Visit – SAF 14.4.5.1 Worsening Shifts in Study Eye Dilated Fundoscopy Results–SAF Worsening Shifts in Fellow Eye Dilated Fundoscopy Results-SAF 14.4.5.2 Summary of Study Eye Intraocular Pressure and Change from Baseline by Visit 14.4.6.1 - SAF Summary of Fellow Eye Intraocular Pressure and Change from Baseline by 14.4.6.2 Visit – SAF Listings 16.2.1 **Subject Disposition** 16.2.2.1 **Inclusion Criterion** 16.2.2.2 **Exclusion Criterion** 16.2.2.4 **Protocol Deviations** 16.2.3.1 Subjects Excluded from the Per Protocol Analysis Set 16.2.4.1 Demographic and Baseline Information 16.2.4.2 Ocular Medical History Ocular Surgical History 16.2.4.3 16.2.4.4 Non-ocular Medical History 16.2.4.5 Non-ocular Surgical History Dosing Compliance and Exposure 16.2.5.1 16.2.5.2 Dispense Investigational Drug Daily Dosing Diary 16.2.5.3 Randomized and Actual Treatments 16.2.5.4 16.2.6.1 Corneal Fluorescein Staining (CFS) by Area and Total Score 16262 Dryness Score (VAS) Ocular Symptoms (VAS) 16.2.6.3 16.2.6.4 Ocular Surface Disease Index (OSDI) 16.2.6.5 Meibomian Gland Assessment (MGD Score) 16.2.6.6 Schirmer's Test I (Without Anesthesia) Tear Film Break-up Time (TFBUT) 16.2.6.7 16.2.6.8 **Instillation Comfort Questionnaire** 16.2.6.9 **Evedrop Acceptability Questionnaire** Collection of Returned Investigational Product 16.2.6.10 All Adverse Events by SOC, PT, and Verbatim Term 16.2.7.1 Adverse Events Leading to Premature Discontinuation of Treatment 16.2.7.2 Serious Adverse Events 16.2.7.3 16.2.7.4 **Subject Deaths Pregnancy Test** 16.2.8.1 Visual Acuity 16.2.9.1

Protocol Number: 904

6.2.9.2	Slit-lamp Biomicroscopy
6.2.9.3	Dilated Fundoscopy
6.2.9.4	Intraocular Pressure
6.2.9.5	Ocular Concomitant Medications
6.2.9.6	Ocular Concomitant Therapies
6.2.9.7	Non-ocular Concomitant Medications
6.2.9.8	Non-ocular Concomitant Therapies
6.3.1	Unscheduled Visits
6.3.2	Subject Completion

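### Eye-exam results from unscheduled safety visits fall outside the by-visit safety tables, and whether they enter the worsening-shift tables is unclear, so transient worsening can be missed, most readily for IOP and fundoscopy.

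*Protocol*

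**What the plan says.** **Collection.** Protocol 8.4.3 allows extra visits: "An unscheduled visit may be performed during the course of the trial in order to ensure subject safety", or to resupply study drug. Slit-lamp, visual acuity, IOP and dilated fundoscopy are among the evaluations that may be carried out. The results are captured: "All procedures performed at an unscheduled visit will be recorded in the source documents and on the unscheduled visit eCRF pages".

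**Visit rule.** SAP 6.5.8.2 states "The eCRF nominal study visits will be used for analysis", and then "For the purposes of table summarization, the first visit for each nominal study visit will be used". For subjects who withdraw, it places data from a regular visit under that visit, but "if they withdraw between scheduled visits, the early termination visit will be treated as an unscheduled visit".

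**Safety summaries.** The sentence in SAP 6.5.9.4 that covers all four exams ends "intraocular pressure will be summarized by treatment group and visit using descriptive statistics in SAF". Protocol 10.4.10 specifies the same by-visit layout. For IOP, SAP 6.5.9.4.4 says "the results will be recorded in mmHg at screening, Visit 4 and early termination", and SAP 6.5.9.4.3 gives fundoscopy the same schedule. Slit-lamp and acuity are done at every visit. No subsection defines a worst or any-time post-baseline value.

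**Outputs.** In SAP Section 7, tables 14.4.1, 14.4.2, 14.4.4 and 14.4.6 are titled by visit. The worsening-shift tables 14.4.3 (slit-lamp) and 14.4.5 (fundus) have no visit in their titles. The only planned output that names these extra visits is a listing, "Unscheduled Visits".

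**The concern.** Protocol 6.2 lists five safety endpoints, and four of them are these eye exams. Safety is compared descriptively only (protocol 10.4.10, SAP 6.5.9.1.7), so the 14.4 tables are the planned between-arm comparison for those four endpoints.

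An exam at a safety-driven unscheduled visit is done because there may be a problem. Under the nominal-visit rule, its result does not count in the by-visit tables. If the finding has resolved by the next scheduled exam, those tables show that eye as unchanged. A short-lived corneal finding, IOP rise or small acuity loss could then be documented on the eCRF and absent from the exam tables.

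The point concerns subjects who continue in the trial. How early-termination visits are handled is a separate matter.

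**Working it through.** The plan gives no figure to reproduce. The check follows an unscheduled result from collection to output.

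1. **Is it collected?** Yes, on its own eCRF pages (protocol 8.4.3).
2. **Is it assigned to an analysis visit?** No. SAP 6.5.8.2 uses the nominal eCRF visit and has no window rule that would move an unscheduled record to a scheduled visit. Its treatment of withdrawals sets data placed under a regular visit against data treated as unscheduled, which implies that unscheduled data are not placed under a regular visit.
3. **Does a by-visit table show it?** No. Tables 14.4.1, 14.4.2, 14.4.4 and 14.4.6 are laid out by visit and use the first record of each nominal visit.
4. **Does a shift table show it?** Unclear. SAP 6.5.9.4.2 and 6.5.9.4.3 say that worsening shifts are summarised without saying at which visit or from which record. If the general rule in 6.5.8.2 applies, unscheduled exams are out. Two things pull the other way: SAP 6.5.9.4.1 to 6.5.9.4.4 say the statistics cover every visit after baseline, and the shift-table titles are not tied to a visit.
5. **Does any other table show it?** Only if the finding is recorded as an adverse event (AE).

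The time during which a transient finding can go unseen follows from the schedule (protocol Appendix 1, SAP Table 1), using nominal days:

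| Exam | Scheduled post-baseline exams | Gaps between exams, counted from Day 1 |
|---|---|---|
| Slit-lamp, acuity | Days 15, 29, 57 | 15 − 1 = 14; 29 − 15 = 14; 57 − 29 = 28 days |
| IOP, fundoscopy | Day 57 only | 57 − 1 = 56 days |

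With the ±2-day window, Visit 4 falls on Day 55 to 59, so the IOP and fundus gap is 54 to 58 days. For a continuing subject, every IOP or fundus exam between first dose and Visit 4 is therefore unscheduled.

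The AE route differs by exam. Protocol 9.1 makes a rise of 0.22 or more in logMAR from Visit 0 an AE by rule. It gives no numeric threshold for IOP, slit-lamp or fundus findings, so for these the route depends on the investigator recording the sign as an AE.

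The documents give no rate of unscheduled visits. As an assumption only, suppose 1% to 5% of 280 subjects per arm have a safety-driven exam and half of those show a worsening that resolves before the next scheduled exam. Then 280 × 0.01 × 0.5 = 1.4 and 280 × 0.05 × 0.5 = 7, or about 1 to 7 subjects per arm. This range restates its two assumptions and is not an estimate from the plan.

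**The case against.** The strongest reply is that the safety information is not lost. Assessment of AEs is itself on the unscheduled-visit list in protocol 8.4.3. Protocol 9.1 defines an AE broadly enough to include any unfavourable sign, and requires documentation of signs the physician observes. The treatment-emergent AE tables are not tied to visits and are split by study eye and fellow eye. By-visit exam summaries are also conventional, and the SAP follows the protocol in using them.

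Much of this stands, and it rules out four stronger readings that a reader might infer:

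- *The findings reach only a listing.* This is not supported. It describes the exam values, but any finding recorded as an AE is also tabulated, and for acuity losses of 0.22 logMAR or more that is automatic.
- *The SAP excludes unscheduled exams from the shift tables.* It never says so. The exclusion is inferred from 6.5.8.2, and the wording in 6.5.9.4.1 to 6.5.9.4.4 leaves room for the opposite reading.
- *The between-arm incidence of ocular worsening is understated.* The by-visit tables report status at scheduled visits and do not claim to give cumulative incidence. Neither the size nor the direction of any between-arm effect can be derived.
- *The protocol requires these exams at every unscheduled visit.* It only permits them, and some such visits are solely for resupply.

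The reply does not close the gap. AE reporting is a different endpoint from the four exams. For IOP, slit-lamp and fundus findings it rests on judgement rather than a stated threshold, and an AE table does not give the measured pressure or exam grade. The ambiguity over the shift tables is itself a defect, because two programmers could produce different tables from the same text.

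**Conclusion.** The point holds in a limited form. Under SAP 6.5.8.2 and 6.5.9.4, unscheduled eye-exam results from continuing subjects are outside the by-visit tables. On the natural reading they are also outside the shift tables, although the text leaves that open. The exam tables can therefore miss transient worsening. The exposure is greatest for IOP and fundoscopy, with one scheduled on-treatment exam and no numeric AE threshold. It is smallest for acuity, where losses of 0.22 logMAR or more are AEs by rule.

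The conclusion assumes that 6.5.8.2 governs the safety tables, since nothing in 6.5.9.4 exempts them. The number of subjects affected and any effect on the comparison between arms are unknown. Efficacy analyses are not touched. This is a worthwhile, inexpensive improvement to the safety reporting and does not threaten the trial's main conclusions.

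**What to change.** Amend the SAP in two places before database lock and unmasking, as SAP Section 4 allows:

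- **6.5.8.2:** state that the nominal-visit and first-record rules govern by-visit summaries and do not apply to the worst post-baseline safety summaries.
- **6.5.9.4:** state that shift tables 14.4.3 and 14.4.5 use the worst post-baseline grade per eye from scheduled or unscheduled exams. Add a worst post-baseline summary by eye and arm giving the largest logMAR increase and the highest IOP.

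Leave the by-visit summaries unchanged. The protocol already sends the data to the eCRF, so nothing new is collected.

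The cost is programming and extra rows. Tables 14.4.1 to 14.4.6 are 6 × 2 = 12 tables, counting study eye and fellow eye, and the graded exams cover six slit-lamp and five fundus locations with three grades each. Because unscheduled exams are driven by events, the new rows also depend on who came for an extra visit. They must be labelled and read as incidence of worsening, not as means at a time point.
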